3.4 Eligibility Criteria

3.4.1 Inclusion Criteria:

- Women older than 18 years at the time of induction of labor with the ability to give informed consent
- Induction of labor for clinical diagnosis of preeclampsia
- Unfavorable cervix (Bishop's score of less than 6) See below
- Cervical dilation 2cm or less
- Singleton
- Gestational age \geq 24 weeks
- English speaking

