Use of Nitrous Oxide Donor for Labor Induction in Women with
PreEclampsia (NOPE)

NCT03171480

November 2017

**Use of Nitrous Oxide Donor for Labor Induction in Women with PreEclampsia or
Gestational Hypertension (NOPE): A Randomized Controlled Trial**

Draft Protocol

[name] MD
The Ohio State Wexner Medical Center
Department of OB/GYN, Maternal Fetal Medicine

November 2017

Version 1.2

1. Introduction

1.1 Background:

Hypertensive diseases of pregnancy, including preeclampsia and gestational hypertension affects at least 5-10% of all pregnancies. Preeclampsia is the most severe form and is a rapidly progressive condition characterized by high blood pressure and the presence of protein in the urine. Gestational hypertension is defined as systolic blood pressure (SBP) >140 mmHg and diastolic blood pressure (DBP) >90 mmHg and approximately half of women diagnosed with gestational hypertension will progress to preeclampsia.

To date there is no cure for preeclampsia except delivery. Given the potential of adverse consequences for both mother and fetus, preeclampsia and gestational hypertension is the leading diagnosis triggering medically indicated preterm birth. Therefore, most patients with gestational hypertension or preeclampsia who require delivery will not be in spontaneous labor and must undergo induction of labor. The obstetrician then faces a dilemma regarding the optimal method of induction. As to date there is no consensus to guide the physician on the best method for induction of labor. The ideal induction agent(s) should result in a relatively short induction to delivery interval without risk to fetus and with low rates of cesarean sections. The induction to delivery interval and low rates of CD is especially important in preeclampsia, to minimize significant maternal and infant morbidity associated with CD and to preventing worsening of disease.

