Specific aim 3: To evaluate the safety of NOD isosorbide mononitrate (IMN) administered at the time of induction of labor in terms of frequency of intrapartum outcomes including placental abruption, need to treat with acute antihypertensive

medications, uterine hyperstimulation, maternal hypotension, atony, side effects (headache, nausea, vomiting, dizziness), and neonatal resuscitation.

3. Study Design

3.1 Primary Research Question:

Does intravaginal administration of NOD isosorbide mononitrate (IMN) as an adjuvant to misoprostol/ intra-cervical Foley bulb for induction of labor decrease the rate of cesarean deliveries in pregnancies complicated by gestational hypertension or preeclampsia?

Hypothesis 1: Compared to placebo, administration of intravaginal IMN as adjuvant to induction of labor decreases rate of cesarean deliveries in pregnancies complicated by gestational hypertension or preeclampsia.

3.2 Secondary Research Questions:

3.2.1 Does use of intravaginal NOD isosorbide mononitrate (IMN) as an adjuvant to misoprostol/ intra-cervical Foley bulb for induction of labor reduce the interval time to delivery?

Hypothesis 2: Compared to placebo, administration of intravaginal IMN at the time of induction of labor reduces the time interval from induction to vaginal delivery.

3.2.2 Is use of intravaginal IMN as an adjuvant induction agent in pregnancies complicated by preeclampsia associated with a favorable risk/benefit ratio?

Hypothesis 3: Administration of intravaginal IMN as an induction agent is safe and not associated with an increased risk of placental abruption, use of anti-hypertensives, maternal hypotension and uterine hyperstimulation, atony, meconium stained fluid compared to placebo, need for neonatal resuscitation.

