3.3 Design Summary

[figure not shown]
We are proposing a double blinded, placebo controlled, randomized clinical trial of patients undergoing induction of labor for gestational hypertension or preeclampsia. Once the decision to induce will be taken, mothers will be randomized to receive either intravaginal IMN (30mg) or identical appearing placebo placed every 4hrs in the posterior vaginal fornix X 3 doses. IMN or placebo will be discontinued when active labor occurs or when the physician decides to proceed with augmentation with oxytocin or AROM. Participants will be induced using our routine induction agents, Misoprostol (25 mcg every 4 hrs for maximum of 6 doses) and an intra-cervical foley bulb will be inserted with 2nd dose of IMN or placebo. See figure 1, for further details. Regarding management of labor, physician decides when to proceed with augmentation with oxytocin or AROM.

An intra-cervical foley bulb will be placed with 2nd dose of IMN (or placebo). If unable to be placed, a higher level provider must attempt placement, if still unable to be placed the patient will be examined every 4 hours and Foley bulb placement was reattempted if Bishop's score is still 6 or less. When the Foley bulb had fallen out, further management of labor will be at the discretion of the labor team and included expectant management, amniotomy, or IV oxytocin. If indicated,

IV oxytocin will be started per standard protocol after 4 hours from the last misoprostol dose. The rest of the obstetrical care will be similar in all arms and guided by clinical guidelines.

Figure 1. Detailed algorithm of enrollment

Isosorbide mononitrate or Placebo Combined with Misoprostol and Foley Protocol

- IMN should be administered intravaginal every 4 hours for maximum of 3 doses
- Misoprostol should be administered intravaginal every 4 hours for maximum of 6 doses, if < 4 contractions in 10 minutes and bishop score <6
- If cervical Foley bulb cannot be placed at initial exam, a second higher level provider must attempt. If still unable to place, repeat exam in 1-2 hours from misoprostol placement to reattempt Foley placement.
- In order to call it a failed placement attempt, an attempt must be made with patient placed in stirrups and under direct visualization.
- Remove Foley if still in place after 12 hours from placement. Can continue with misoprostol use after Foley is removed as long as it meets criteria noted above.

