3.5.2 Screening

Under the direction of the PI, trained research nurses will be available to **screen and consent** patients according to study protocol. We will enroll patients at the time of admission to labor and delivery (L&D) for induction of labor. All patients admitted for induction of labor for preeclampsia will be approached by the research nurses and will be provided with information and consent forms for the study so that if an emergent cesarean delivery is required in the near future the patient will already be informed about the study. Medical records of all potential patients will be reviewed and those who satisfy inclusion and exclusion criteria will be approached for informed consent. A screening and enrollment log will be used to track all patients approached for the study.

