3.5.3 Randomization and Masking

After obtaining informed consent, women undergoing an induction of labor for preeclampsia will be randomized to either 30mg IMN given intravaginal with placement of misoprostol/foley bulb (as clinically indicated) or placebo in a 1:1 ratio. Randomization in each group will be by simple randomization, and will be computer generated. A confidential computer-generated simple randomization will be prepared and provided on an ongoing basis to a designated investigational pharmacist (all other study staff will be blinded). The investigational pharmacy will prepare identical appearing suppositories of IMN (30mg) or placebo according to the randomization sequence and deliver to a dedicated secure area in the labor and delivery area. A randomization log with study medication number, patient name and medical record number will be used to track the randomization process.

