3.5.4 Drug Administration

When the decision is made to proceed with induction of labor for preeclampsia, and after ensuring for a consented patient, an order to give the study medication will be activated and the available study medication will be administered by the provider. The patient is considered randomized once the medication is dispensed. The investigational drug pharmacy will deliver the next study medication to the labor and delivery unit if a subsequent consented patient is already identified.

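### The enrollment sections admit only women induced for preeclampsia, but the title, primary question, control rate and accrual estimate also cover gestational hypertension

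*Combined protocol and SAP*

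**What the plan says.** The sections that staff use to enroll a woman name preeclampsia only:

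- Section 3.4.1, Inclusion Criteria: "Induction of labor for clinical diagnosis of preeclampsia"
- Section 3.5.2, Screening: "All patients admitted for induction of labor for preeclampsia will be approached by the research nurses"
- Section 3.5.3, Randomization and Masking: "women undergoing an induction of labor for preeclampsia will be randomized"
- Section 3.5.4, Drug Administration: "When the decision is made to proceed with induction of labor for preeclampsia"

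The short title, the sentence in Section 5.1 that introduces Table 1, and the risk/benefit question in Section 3.2.2 ("adjuvant induction agent in pregnancies complicated by preeclampsia associated with a favorable risk/benefit ratio") are equally narrow.

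The sections that set the purpose and size of the trial are wider. The primary question in Section 3.1 asks whether the drug will "decrease the rate of cesarean deliveries in pregnancies complicated by gestational hypertension or preeclampsia". Section 3.3 proposes a "randomized clinical trial of patients undergoing induction of labor for gestational hypertension or preeclampsia". The full title, the proposal at the end of Section 1.1, aim 1, Hypothesis 1 and the closing objective in Section 7.0 also name both diagnoses. So do the 295-woman cohort and the 45% control rate in Section 5.1, and the accrual estimate in Section 5.4.

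**The concern.** Screening staff cannot comply with both sets of passages. If they follow Section 3.4.1, no woman with gestational hypertension alone is enrolled. The trial then gives a randomized answer for preeclampsia and none for the other diagnosis in its primary question, while its control rate and accrual come from a wider population than the one enrolled. If they follow the full title, each woman with gestational hypertension alone is an eligibility deviation, and she is still counted under the intent-to-treat analysis in Section 5.5. The diagnosis is not among the baseline variables listed in Section 5.5, so the planned baseline comparison would not show which population was enrolled.

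**Working it through.** **1. Are the two diagnoses different in this document?** Yes. Section 1.1 characterizes preeclampsia by high blood pressure with protein in the urine, defines gestational hypertension by blood pressure thresholds, and says that "approximately half of women diagnosed with gestational hypertension will progress to preeclampsia". The other half would therefore have gestational hypertension alone. No passage defines preeclampsia to include it.

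**2. Does another passage settle eligibility?** No. The exclusion list in Section 3.4.2 does not mention gestational hypertension. The image of Figure 1 is not in the text supplied, and the text under its caption covers dosing and Foley placement, not diagnosis.

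**3. The plan's own accrual figure.** Inputs from Section 5.4: 5000 deliveries per year, 8% with either diagnosis, two thirds induced, 50% consent.

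- Eligible: 5000 × 0.08 × 2/3 = 267 per year. The stated 264 results from taking two thirds as 0.66.
- Randomized: 264 × 0.5 = 132 per year.
- Duration: 400 / 132 = 3.03 years, which agrees with the stated 3 years or so.

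**4. Accrual under the literal criterion.** Let s be the share of the 264 with gestational hypertension alone. The documents do not give s, so the values below are assumptions.

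Randomized per year = 264 × (1 − s) × 0.5. Years = 400 / that number. Consent needed to restore the stated pace = 132 / [264 × (1 − s)].

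| s (assumed) | Randomized per year | Years to 400 | Consent needed for 132 per year |
|---|---|---|---|
| 0 | 132 | 3.03 | 50% |
| 10% | 118.8 | 3.37 | 55.6% |
| 25% | 99 | 4.04 | 66.7% |
| 50% | 66 | 6.06 | 100% |

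Section 5.4 expects consent above 50%, which would offset part of this. Section 6.1 expects 5 to 6 patients per week, that is 5 × 52 = 260 to 6 × 52 = 312 per year. That does not match 132, so the accrual baseline is itself uncertain.

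**5. The plan's own power figure.** Inputs from Sections 5.1 and 3.5.3: 45% control rate, 33% relative reduction, two-sided alpha 0.05, 1:1 allocation, N = 400, 2% loss. So p1 = 0.45, p2 = 0.45 × 0.67 = 0.3015, and n = 200 per arm, or 196 after loss.

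Power = Φ{[(p1 − p2)√n − 1.96√(2p̄(1 − p̄))] / √[p1(1 − p1) + p2(1 − p2)]}, where p̄ = (p1 + p2)/2 = 0.37575.

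- n = 200: (2.100 − 1.342) / 0.677 = 1.119, power 86.9%.
- n = 196: (2.079 − 1.342) / 0.677 = 1.088, power 86.2%.

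The plan's claim of more than 85% reproduces, for the combined population.

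**6. Power if the preeclampsia-only control rate differs.** The documents give no such rate. Over the range of Table 1 columns, with the same 33% relative reduction and 196 per arm:

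| Control rate (assumed) | Power |
|---|---|
| 35% | 71.2% |
| 40% | 79.4% |
| 45% | 86.2% |
| 50% | 91.5% |
| 55% | 95.3% |

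The direction of any change is unknown.

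**The case against.** The strongest reply is that the intention is plain and the narrow wording is shorthand. Both diagnoses appear in the full title, aim 1, primary question, Hypothesis 1, design summary, control rate, accrual and conclusion. In Section 5.1 the 45% rate is given for both, and the next paragraph describes the same calculation as being for preeclampsia. Only Section 3.4.1 is an eligibility criterion; Sections 3.5.2 to 3.5.4 describe procedures. Neither reading biases the comparison between arms, and if both diagnoses are admitted, nothing in power or accrual changes. The accrual shares are assumed, and Table 1 already shows how sample size depends on the control rate.

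Much of this stands. Incompletely updated wording is a plausible explanation. The accrual and power scenarios apply only if the criterion is followed literally, and they are ranges rather than estimates. The mismatch between the weekly and yearly enrollment figures is a separate matter. The list in Section 5.5 is labelled as demographic data, so adding the diagnosis is a recommendation, not the correction of an error.

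The central point is unaffected. An inclusion criterion is applied as written, and the same restriction recurs in three procedural sections. A clear intention makes the repair easy; it does not change what the criterion says.

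**Conclusion.** The concern holds. From the text alone, every woman induced for gestational hypertension without preeclampsia fails Section 3.4.1, although the primary question, control rate and accrual estimate include her. This must be fixed, because it determines whom the primary result describes. It does not threaten the validity of the randomized comparison.

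Confidence in the contradiction is high. The practical size cannot be fixed from the documents. Enrollment ranges from 3.0 years if nobody counted is excluded to about 6.1 years if half are, at 50% consent and 264 counted women per year. Power for 400 women could be lower or higher than the stated figure. If the criteria are widened to the stated population, accrual and power stand as stated.

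**What to change.** Choose one population and make every passage agree with it.

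1. **If both diagnoses are intended:** name both in Sections 3.4.1, 3.5.2, 3.5.3 and 3.5.4, in the Section 3.2.2 question and in the Table 1 sentence of Section 5.1. Align the short title too, if it is meant to describe the population. Recording the diagnosis at randomization and adding it to the Section 5.5 baseline variables is advised, so that the enrolled mix can be reported. Cost: six wording changes, the short title if wanted, and one data field. No extra patients are needed.
2. **If preeclampsia only is intended:** restate the full title, the proposal in Section 1.1, aim 1, the primary question, Hypothesis 1, Section 3.3 and Section 7.0. Obtain a preeclampsia-only control rate and eligible count, then recompute power and accrual in Sections 5.1 and 5.4. Cost: a further look at the source data, possibly a different sample size, and possibly a longer enrollment period.

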3.4.1.1 Bishop Score

The Bishop Score is the most commonly used method to rate the readiness of the cervix for induction of labor. The Bishop Score gives points to 5 measurements of the pelvic examination dilation, effacement of the cervix, station of the fetus, consistency of the cervix, and position of the cervix. The link below has a calculator that examiner will use to calculate a Bishop score prior to randomization.

<http://perinatology.com/calculators/Bishop%20Score%20Calculator.htm>

CERVICAL EXAM	POINTS				SUBSCORE
	0	1	2	3	
Dilation (cm)	Closed 	1-2 cm 	3-4cm 	5 - 6cm 	
Effacement (%)	0-30% 	40-50% 	60-70% 	80% 	
Station	-3 	-2 	-1, 0 	+1, +2 	
Consistency	Firm 	Medium 	Soft 		
Position	Posterior 	Mid 	Anterior 		
					
BISHOP'S SCORE 					

3.4.1.2 Gestational Age Determination

Gestational age is determined in the following manner and is denoted as “project gestational age (GA).” The “project estimated date of confinement (EDC),” which is based on the project GA, cannot be revised once a determination has been

made. Because the project EDC depends on information from the earliest dating ultrasound, if no ultrasound has been performed previously, one must be performed before the patient can be enrolled.

1. The first day of the last menstrual period (LMP) is determined and a judgment is made as to whether or not the patient has a “sure” LMP date.

2. If the LMP date is unsure, the ultrasound measurements obtained at the patient’s first ultrasound examination are used to determine the project GA by the standard method of ultrasound GA determination at that institution.

3. If the LMP date is sure and the ultrasound confirms this GA within the number of days specified in Table 3 1, then the LMP-derived GA is used to determine the project GA.

4. If the ultrasound-determined GA does not confirm the LMP-generated GA within the number of days specified in Table 3-1, then the ultrasound is used to determine the project GA.

Table 3-1. Cutoffs for Using LMP to Determine Gestational Age

Gestational age range at first ultrasound by LMP	Method of Measurement	Ultrasound agreement with LMP
≤ 8 6/7 weeks	CRL	± 5 days
9 0/7 weeks to 13 6/7 weeks	CRL	± 7 days
14 0/7 weeks to 15 6/7 weeks	BPD, HC, AC, FL	± 7 days
16 0/7 weeks to 21 6/7 weeks	BPD, HC, AC, FL	± 10 days
22 0/7 weeks to 27 6/7 weeks	BPD, HC, AC, FL	± 14 days
28 0/7 weeks and beyond	BPD, HC, AC, FL	± 21 days

3.4.2 Exclusion Criteria:

- Contraindication to vaginal delivery
- Contraindication to misoprostol
- Fetal Demise
- Major fetal anomaly
- Non-english speaking women
- HIV
- Medical conditions requiring assisted second stage
- Category III tracing
- Eclampsia
- Hemolysis Elevated Liver enzymes Low Platelets syndrome
- DIC or active hemorrhage before randomization
- Hypersensitivity to isosorbide mononitrate
- Isosorbide mononitrate should not be used in cases of acute myocardial infarction with low filling pressure, acute circulatory failure (shock, vascular collapse), or hypertrophic obstructive cardiomyopathy (HOCM), constrictive pericarditis, low cardiac filling pressures, aortic/mitral valve stenosis and diseases associated with a raised intra-cranial pressure e.g following a head trauma and including cerebral hemorrhage.
- Isosorbide mononitrate should not be used in patients with severe anemia, severe hypotension, closed angle glaucoma or severe hypovolaemia.

- Isosorbide mononitrate tablets contain lactose and therefore patients with rare hereditary problems of galactose intolerance, the Lapp lactase deficiency or glucose-galactose malabsorption should not take this medicine.

3.5 Study Procedures

3.5.1 Informed consent

Written informed consent must be obtained from patients before they can be randomized into the study. Full disclosure of the nature and potential risks of participating in the trial are to be made. Consent forms will be according to the requirements of the IRB and are required by the Health Insurance Portability and Accountability Act (HIPAA) Privacy Rule. Women who are not fluent in English will not be enrolled. A copy of the signed consent form will be provided to the patient.

3.5.2 Screening

Under the direction of the PI, trained research nurses will be available to **screen and consent** patients according to study protocol. We will enroll patients at the time of admission to labor and delivery (L&D) for induction of labor. All patients admitted for induction of labor for preeclampsia will be approached by the research nurses and will be provided with information and consent forms for the study so that if an emergent cesarean delivery is required in the near future the patient will already be informed about the study. Medical records of all potential patients will be reviewed and those who satisfy inclusion and exclusion criteria will be approached for informed consent. A screening and enrollment log will be used to track all patients approached for the study.

3.5.3 Randomization and Masking

After obtaining informed consent, women undergoing an induction of labor for preeclampsia will be randomized to either 30mg IMN given intravaginal with placement of misoprostol/foley bulb (as clinically indicated) or placebo in a 1:1 ratio. Randomization in each group will be by simple randomization, and will be computer generated. A confidential computer-generated simple randomization will be prepared and provided on an ongoing basis to a designated investigational pharmacist (all other study staff will be blinded). The investigational pharmacy will prepare identical appearing suppositories of IMN (30mg) or placebo according to the randomization sequence and deliver to a dedicated secure area in the labor and delivery area. A randomization log with study medication number, patient name and medical record number will be used to track the randomization process.

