- neonatal blood transfusion

- hypoxic–ischemic encephalopathy
- intraventricular hemorrhage grade 3 or 4
- necrotizing enterocolitis
- receipt of head cooling
- Other neonatal outcomes analyzed will be neonatal intensive care unit admission, neonatal intensive care unit admission greater than 48 hours, and neonatal length of stay (days).

5. Statistical Considerations

5.1 Sample size calculation:

Using data from our prior studies using the intended study population at The Ohio State Wexner Medical Center the incidence of gestational hypertension or preeclampsia is 10-15%.

Data abstracted from those enrolled in biorepository for gestational hypertension or preeclampsia over one year period and excluding those who were delivered for gestational hypertension or preeclampsia who had cesarean section for breech, prior cesarean section or uterine surgery, HELLP syndrome, eclampsia.

295 women underwent induction of labor for gestational hypertension or preeclampsia 48% (n=141) ended up with cesarean delivery after failed induction of labor or non-reassuring fetal well being.

Gestational Age Distribution for Gestational Hypertension or Preeclampsia Induction

Gestational Age in weeks	Number of women IOL for gHTN or PE	CS rate
24-28 wks	13	10 (77%)
28-30 wks	15	11 (73%)
30-32 wks	26	18 (69%)
32-34 wks	39	19 (49%)
34-36 wks	56	20 (34%)
36-37 wks	35	12 (34%)
37-38 wks	57	22 (38%)
38-39 wks	17	3 (18%)
39-40 wks	8	2 (25%)
40-41 wks	2	1 (50%)

Review of literature reveals is similar to OSU numbers, with the overall rate of cesarean delivery after induction of labor for gestational hypertension or preeclampsia ranges from 40% to 70%. Based on available data, we anticipate that the expected rate of the primary outcome in the women undergoing induction of labor for gestational hypertension or preeclampsia 45%. For this proposal, we will estimate a conservative relative reduction effect of 30-35%.

The table below provides the sample size calculations needed to achieve 80-90% power to detect 30-35% difference in the primary outcome between women receiving IMN or placebo at time of their induction of labor for preeclampsia, using a two-tailed alpha of 0.05.

Table 1. Total sample size required to detect a difference in primary outcome in women undergoing induction of labor and receiving IMN or placebo (alpha at 0.05, variable primary outcome rates, power, and effect sizes)

Relative reduction (%)	Power (%)	Primary Outcome Rate in Placebo group				

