		35%	40%	45%	50%	55%
30	90	784	644	540	462	380
	85	670	550	460	394	326
	80	586	480	404	346	284
33	90	656	540	430	368	306
	85	562	462	368	316	276
	80	490	404	322	276	242
35	90	586	482	406	330	290
	85	502	412	348	282	248
	80	438	362	304	248	216

Assuming the primary outcome to be 45 %, close to 1:1 enrollment and anticipating that no more than 2% of randomized women to be lost to follow up, a sample size of 400 women will achieve >85% power to detect a 33% relative reduction in primary outcome overall.

Given the study design and that randomization will occur once decision to proceed with induction occurs, there will be no concern for loss to follow up or missing outcome data on any women. Regarding concern for non-compliance, given study design we propose that it is unlikely that participant would not get their assigned treatment.

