5.2 Interim Analysis

Interim statistical analyses of clinical trials will be at least once a year to review trial results; however, the exact timing of the interim analyses is at the discretion of the PI. A formal detailed statistical report will be written by the PI which presents the results of every aspect of the study, including all baseline variables, protocol adherence, all outcome variables, adverse events reported and center performance in terms of recruitment, data quality, loss to follow-up and protocol violations. However, the main emphasis is on the primary outcome as well as maternal safety outcomes. It is recognized that any decision to terminate the study would not be reached solely on statistical grounds but on a number of complex clinical and statistical considerations.

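### Gestational age, a strong predictor of cesarean known before randomization, is used in neither the allocation nor a pre-specified analysis; fixing a stratified comparison would raise power from about 86% to about 88%

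*Combined protocol and SAP*

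**What the plan says.** - **Allocation (3.5.3).** Women are assigned to IMN "or placebo in a 1:1 ratio", and "Randomization in each group will be by simple randomization, and will be computer generated". No blocks or stratification factors are named anywhere.
- **Predictor (5.1).** The table headed "Gestational Age Distribution for Gestational Hypertension or Preeclampsia Induction" gives women and cesareans by gestational age. Section 3.4.1.2 requires project gestational age to be settled before enrolment and not changed afterwards.
- **Sample size (5.1).** The calculation was made "using a two-tailed alpha of 0.05". The conclusion begins "Assuming the primary outcome to be 45 %, close to 1:1 enrollment", allows for "no more than 2% of randomized women to be lost to follow up", and states that "a sample size of 400 women will achieve >85% power to detect a 33% relative reduction in primary outcome overall".
- **Interim looks (5.2).** "Interim statistical analyses of clinical trials will be at least once a year to review trial results". Timing is left to the principal investigator, and the emphasis is on the primary outcome and maternal safety.
- **Analysis (5.5).** Gestational age at randomization is among the baseline variables to be tested for homogeneity. Outcomes are then analysed by univariable and multivariable methods according to need. No model, covariate or trigger for adjustment is stated.

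**The concern.** When a baseline variable separates women with a 62% risk of the primary outcome from women with a 34% risk, leaving it out of both allocation and analysis has two consequences. Variation that could be removed stays in the standard error. And in any single trial, part of the observed cesarean difference may reflect who was allocated where.

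The second matters most at the yearly looks, when numbers are small and 5.2 gives no statistical boundary. With a homogeneity test planned and adjustment left open, the team could also decide whether to adjust for gestational age after seeing the imbalance and both versions of the result. Fixing the choice beforehand removes that freedom.

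**Working it through.** **1. The plan's own power.** Inputs from 5.1: control rate 0.45; 33% relative reduction, so 0.45 × 0.67 = 0.3015 (difference 0.1485); 400 women less 2% = 392, or 196 per arm; two-sided alpha 0.05. Mean rate 0.37575.

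z = [0.1485 − 1.96 × √(2 × 0.37575 × 0.62425 / 196)] / √[(0.45 × 0.55 + 0.3015 × 0.6985) / 196] = (0.1485 − 0.0959) / 0.0483 = 1.09, so power is 86.2%. The stated figure is reproduced.

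**2. Strength of the predictor.** Counts from the 5.1 table:
- Below 34 weeks: 13 + 15 + 26 + 39 = 93 women; 10 + 11 + 18 + 19 = 58 cesareans (62.4%).
- 34 weeks or later: 56 + 35 + 57 + 17 + 8 + 2 = 175 women; 20 + 12 + 22 + 3 + 2 + 1 = 60 cesareans (34.3%).
- Total: 268 women, 118 cesareans (44.0%). Gap 28.1 points; share below 34 weeks 93/268 = 0.347.

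Variance explained by the two strata: 0.347 × 0.653 × 0.281² / (0.440 × 0.560) = 7.25%. Using all ten rows, the between-row variance is 0.02537, and 0.02537 / 0.2464 = 10.3%.

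**3. Shift from chance imbalance.** Under simple 1:1 allocation, the SD of the shift in the cesarean difference due to gestational-age mix alone is √(4 × 0.02537 / N). The SD of the between-arm difference in the share below 34 weeks is √(4 × 0.347 × 0.653 / N). Section 5.4 gives 132 women a year, so yearly looks fall at about 132 and 264. Tail probabilities are from 200,000 simulated trials per size.

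| N | SD of shift (points) | Shift > 3 | Shift > 5 | Share < 34 wk differs ≥ 5 points | ≥ 10 points |
|---|---|---|---|---|---|
| 132 | 2.8 | 28% | 7% | 55% | 23% |
| 264 | 2.0 | 13% | 1.1% | 40% | 9% |
| 392 | 1.6 | 6% | 0.2% | 30% | 4% |

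A 10-point imbalance in the share below 34 weeks moves the cesarean difference by 0.10 × 28.1 = 2.8 points.

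**4. Which change gives the gain.** Trials of 392 women were simulated with the table's mix, rates rescaled to 45% overall, and a 33% relative reduction. The adjusted test is Mantel-Haenszel with strata below 32, 32–34, and 34 weeks or later.

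| Allocation and test | Type I error | Power |
|---|---|---|
| Simple, unadjusted | 5.0% | 86.4% |
| Simple, adjusted | 5.1% | 88.5% |
| Stratified, adjusted | 5.0% | 88.4% |

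A repeat simulation with only the two strata proposed below (simple allocation, 100,000 trials) gave 88.0%. The gain therefore comes from the analysis, not from the allocation.

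**5. What a split at 34 weeks leaves.** It accounts for 7.25 / 10.3, or about 70%, of the shift variance. At 132 women the two-stratum part has SD 8.29% × 0.281 = 2.33 points, leaving √(2.77² − 2.33²) = 1.5 points from differences within strata.

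**The case against.** The strongest reply is that nothing here is an error. Simple randomization is valid, chance imbalance is already counted in the unadjusted standard error, the simulated type I error stays at 4.9–5.0% at all three sizes, and the power claim is met. All of that stands.

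A reader might infer more, in four ways that the documents do not support.
- **That serious imbalance is likely at the yearly looks.** Only a 5-point difference in the share below 34 weeks is more likely than not, and only at 132 women. It moves the cesarean difference by 0.05 × 28.1 = 1.4 points. A 10-point difference has 23% probability at most.
- **That every maternal and neonatal outcome would shift.** The documents tabulate gestational age against cesarean alone.
- **That risk runs dependably from 77% to 18%.** Those are 10/13 and 3/17. The split at 34 weeks rests on larger numbers.
- **That the reference to each group in 3.5.3 points to missing strata.** It may be loose wording for the two arms.

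It is also fair that 5.5 already compares gestational age at baseline and permits multivariable analysis. But it does not say whether or how gestational age will enter the comparison, so the choice remains open. Finally, stratified allocation is not free. The next kit is delivered to the unit in advance (3.5.4), and the pharmacy may hold only seven days' non-patient-specific stock, planned at 20 units (6.1).

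**Conclusion.** A modest improvement is available; the design is not invalid. Pre-specifying a comparison stratified by gestational age adds about 2 points of power (86% to 88%) and removes the option of adjusting only after an imbalance is seen. The shift it guards against is small at the end (SD 1.6 points, 95% within 3.2) and larger at 132 women (SD 2.8, 95% within 5.5), against a target of about 15.

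Assumptions:
- The trial's gestational-age mix and rates match the 268 tabulated women. The text of 5.1 reports 295 women and 141 cesareans, so 27 women and 23 cesareans are not in the table. Placing them all below 34 weeks gives 81/120 v 60/175, a gap of 33 points; placing them all at or above gives 58/93 v 83/202, a gap of 21.
- Counts are used where printed percentages differ (20/56 is 36%, printed as 34%). The 34–36 week row is taken to start at 34 0/7.
- Looks fall at about 132 and 264 women. At the 5–6 women per week expected in 6.1 (260–312 a year), the first look would already resemble the 264 row.

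**What to change.** **Main change, in 5.5.** State that the primary comparison of cesarean rates, at each interim look and at the end, is stratified by project gestational age (below 34 0/7 v 34 0/7 weeks or more), for example by a Mantel-Haenszel test and estimate, whatever the baseline homogeneity tests show. Give the unadjusted result as supportive. This costs a sentence or two and uses a value already collected.

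**Optional change, in 3.5.3.** Stratify the allocation by the same factor, using 1:1 permuted blocks of randomly varying size on a list held by the investigational pharmacist. This protects balance at early looks and in unadjusted secondary comparisons but adds no measurable power. It should not be adopted without the stratified analysis: with allocation stratified, the unadjusted test of cesarean was conservative in simulation (type I error 3.8% at 392). The costs are a new list, slightly more predictable allocation, and either a kit sequence per stratum or the stratum stated on the order, within the stock limit in 6.1.
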